9.3 Withdrawal and Discontinuation

Any subject may voluntarily withdraw (ie, reduce the degree of participation in the study) consent for continued participation and data collection. The reason for withdrawal will be recorded on the End of Study eCRF. Assessments to be performed at the end of study visit (including in cases of withdrawal or discontinuation) are described in Section 10.6 and Section 20.3.

Discontinuation (ie, complete withdrawal from study participation) may be due to dropout (ie, active discontinuation by subject) or loss to follow-up (ie, discontinuation by subject without notice or action). Additionally, the investigator and sponsor have the discretion to discontinue any subject from the study if, in their judgment, continued participation would pose an unacceptable risk for the subject.

Subjects also may be withdrawn from treatment or discontinued from further study participation for the following reasons:

- The subject develops a confirmed high responder inhibitory antibody to FVIII (>5 BU by Nijmegen modification of the Bethesda assay) or a low responder inhibitory antibody (≤ 5 BU but ≥ 0.6 BU) that cannot be managed by the protocol-required treatment.
- The subject experiences a severe anaphylactic reaction to BAX 855.
- The subject requires therapy with another PEGylated product (eg, PEG-Interferon).
- The subject frequently misses administration of IP (ie, misses more than 30% of planned prophylactic doses within any 3-month period).
- The subject is non-compliant with study procedures, in the opinion of the investigator.

- The subject repeatedly uses another FVIII therapy for prophylaxis (in the absence of an acceptable justification to the sponsor) or for the treatment of bleeding episodes.
- The subject requires a surgical or dental procedure and is not eligible or does not consent for the surgery study, or participates in the surgery study and then refuses to resume participation in this continuation study. If the surgery study is closed, the subject will be withdrawn from the continuation study.
- The subject experiences a life-threatening bleeding episode (eg, any gastrointestinal hemorrhage or intracranial hemorrhage).
- The subject experiences severe trauma or requires emergency surgery with FVIII replacement therapy other than BAX 855.
- The subject becomes pregnant. IP exposure will be discontinued. Attempts will be made to follow the subject through completion of the pregnancy and up to 1 year post-delivery, if feasible. The investigator will record a narrative description of the course of the pregnancy and its outcome.

10. STUDY PROCEDURES

10.1 Informed Consent and Enrollment

Any patient and/or patient's legally authorized representative who provides informed consent and, as appropriate, any patient who provides assent (ie, signs and dates the informed consent form and assent form, if applicable) is considered enrolled in the study.

10.2 Subject Identification Code

The following series of numbers will comprise the SIC: protocol identifier (eg, 261203) to be provided by the sponsor, a 3-digit number study site number (eg, 002) to be provided by the sponsor, and 3-digit subject number (eg, 003) reflecting the order of enrollment (ie, signing the informed consent form). For example, the third subject who signed an informed consent form at study site 002 will be identified as Subject 261203-002003. All study documents (eg, eCRFs, clinical documentation, sample containers, drug accountability logs, etc.) will be identified with the SIC. Additionally, a uniquely coded SIC(s) is permitted as long as it does not contain a combination of information that allows identification of a subject (eg, collection of a subject's initials and birth date would not be permitted), in compliance with laws governing data privacy.

10.3 Screening and Study Visits

The study site is responsible for maintaining an enrollment/screening log that includes all subjects enrolled. The log also will serve to document the reason for screening failure. If

a subject does not satisfy all screening criteria, the same subject may be re-screened at a later date. A complete or partial re-screen may also become necessary at the discretion of the investigator or sponsor. All screening data will be collected and reported in eCRFs, regardless of screening outcome. For the purpose of analysis, only the data from the most recent screening visit will be used. If a subject is re-screened, the End of Study eCRF should be completed, and a new ICF, new SIC and new eCRF are required for that subject. The screening procedures including laboratory evaluations must be completed within 45 days or repeated if more than 45 days have elapsed. Exemptions may be granted for administrative reasons, eg delay in timely availability of laboratory results.

The overall study design is illustrated in the [Figure 1](#). A flow diagram of required procedures is presented in [Supplement 20.2](#). Details on the procedures to be performed at each study visit, including screening, can be found in [Supplement 20.3](#) Schedule of Study Procedures and Assessments and [Supplement 20.4](#) Clinical Laboratory Assessments.

10.3.1 Subjects Transitioning from Other BAX 855 Studies

Subjects transitioning from other BAX 855 studies can use the end of study assessments in their previous BAX 855 study for screening visit assessments in this continuation study. Any additional required screening assessments will be performed the same day. Subjects will return to the study site no later than 6 (\pm 1) weeks after the end of study visit in their prior study/continuation study's screening visit to confirm eligibility.

Additionally, transitioning subjects will receive IP treatment either as part of the IR determination of the end of study visit of the previous BAX855 study or the first IP treatment will be given at the screening visit of this continuation study to subjects transitioning from other BAX 855 studies.

Transitioning subjects^x who decide to receive a PK-tailored treatment regimen will continue receiving their study-specific treatment regimen with BAX 855^{xi} (eg, twice weekly 45 ± 5 IU/kg) until baseline/start of PK-tailored prophylaxis. The study-specific prophylactic treatment regimen will be interrupted by one infusion for PK determination in those subjects for whom PK is not yet available.

x As well as subjects who are already participating in the continuation study.

xi NOTE: This refers to the type of treatment that subjects will receive with BAX 855 from this continuation study (not from the previous BAX 855 study).

10.3.2 BAX 855 Naïve Subjects

BAX 855 naïve subjects will continue using their FVIII concentrate and treatment regimen until baseline/start of prophylaxis, except for one infusion with BAX 855 for PK determination (for subjects receiving a PK-tailored prophylactic treatment regimen).

10.4 Medications and Non-Drug Therapies

The following medications are **not** permitted within 30 days before study entry and during the course of the study:

- Any PEGylated medication (eg, PEG-interferon)
- Any investigational drug, biologic, or device, except BAX 855 in case of transitioning subjects

A subject who has taken any of these medications will be considered a protocol deviation.

The use of any FVIII concentrate other than BAX 855 during the course of the study following the first BAX 855 infusion^{xii} will result in the immediate withdrawal of the subject. Every effort should be made to have the Completion/Termination Visit performed. The use of (commercial) ADVATE may be permitted for a short period of time for administrative reasons.

The following medications and non-drug therapies are permitted before study entry and during the course of the study:

- Medications:
 - Hemostatic agents, such as tranexamic acid, are permitted, as indicated by the subject's treating physician, to treat mucosal bleeding during the study
 - Any medications deemed necessary by the subject's physician to treat or prevent any medical condition
 - Any over-the-counter medication used by the subject to treat symptoms or signs
 - Supplemental vitamins, minerals
- Non-drug therapies:
 - Any non-drug therapy (eg, physiotherapy) deemed necessary by the subject's physician to treat or prevent any medical condition

^{xii} This infusion may be the first prophylactic infusion or infusion for the determination of IR for FVIII activity.

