#### 2. STUDY DESIGN

This is a phase 3b, prospective, open label, multi-center study to evaluate the safety and efficacy of BAX 855 for prophylactic use and the control of bleeding episodes in approximately 200 pediatric and adult PTPs  $\leq$  75 years of age with severe hemophilia A. In the Russian Federation, safety and efficacy are only to be assessed in adults aged  $\geq$  18 and < 75 years at the time of enrollment. The study plans to include subjects from other BAX 855 studies and BAX 855-naïve subjects.

Subjects are to receive either a fixed dose prophylaxis with BAX 855 consisting of  $45 \pm 5$  IU/kg for subjects aged  $\geq 12$  years or  $50 \pm 10$  IU/kg for subjects aged  $\leq 12$  years (in all countries except the Russian Federation) twice weekly or, subjects can decide to receive a pharmacokinetic (PK)-tailored prophylactic BAX 855 dosing regimen based on the subject's individual PK to maintain FVIII trough levels of  $\geq 3\%$ . Other treatment regimens were allowed prior to protocol amendment four.

Subjects are to be treated on the specified prophylactic treatment regimen until they reach at least 100 exposure days (EDs) (as accumulated across all BAX 855 studies).

It is to be noted that the use of any FVIII concentrate other than BAX 855 during the course of the study following the first BAX 855 infusion is not permitted. The use of (commercial) ADVATE may be permitted for a short period of time for administrative reasons. It is also to be noted that ADVATE was allowed as rescue medication in

previous versions (prior to amenmdent four) of the protocol for this study under which a number of subjects have been enrolled.

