#### 4.4 Per Protocol Analysis Set (PPAS)

The per protocol (PPAS) analysis set is to comprise all subjects in the FAS who had no major deviations from the protocol affecting the study results. Protocol deviations are to be obtained from the Clinical Trial Management System (CTMS).

Prior to performing any analysis as set out in this SAP, a meeting is to be held discussing the impact of any major protocol deviation on the analysis. At this meeting, the decision is to be made on whether a subject is to be excluded from the PPAS analysis set or not. The meeting is to be attended by participants from at least Biostatistics and Medical.

Below is a list of possible major deviations that may influence the study results that will be discussed at the analysis set assignment meeting:

- Subject less than 75% exposed to BAX 855 as derived in Section 6.8: Measurements of Treatment Compliance.
- Subject less than 75% compliant to planned dosing regimen.
- More than 10% of treated bleeds have no efficacy rating.
- Use of expired IP.
- Subject did not reach 100 EDs across all BAX 855 studies.
- Use of any FVIII product other than ADVATE, as determined by the medical team.

It should be noted that the above will not necessarily lead to immediate exclusion from the PPAS, but will be discussed prior to locking the database. The database is not allowed to be locked until final approval on the PPAS has been obtained.

During the course of the study, data review meetings are to be held on a regular basis. During these meetings the quality of the data including any potential protocol deviations are to be identified. All protocol deviations identified at these meetings are to be included into the CTMS upon team agreement.

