## 6.7 Extent of Exposure

The following information is to be obtained from the eCRF:

- Information on study infusions (*Study Infusions* eCRF panels).
- Treatment regimen, including planned dose (*Treatment Assignment* and *Change of Treatment Assignment* eCRF panels).
- Body weight (*Vital Signs* eCRF panels).

The following derivations based on eCRF reported results are to be performed:

- Body weight-adjusted dose (IU/kg) is to be derived as the total units infused (IU) divided by the last available body weight (kg) prior to the infusion. Refer to Section 5.4: Handling of Missing, Unused, and Spurious Data for imputation schemes to be implemented.
- Total number of infusions in this study are determined as the count of the number of infusions, regardless of date and time, the subject had. Number of infusions are to be determined overall and by reason for infusion as well as by the treatment regimen assigned to at the time of receiving the treatment.
- The number of EDs are determined as the number of unique calendar days on which a subject received any or part of any infusion. Multiple infusions on the same day are still to be considered one ED. EDs are to be determined overall as well as for each reason an infusion is given. The number of EDs will be determined for this study and across all previous BAX 855 studies the subject participated in. EDs in this study will be derived as the number of infusions on unique calendar days in this study, while EDs from previous BAX 855 studies will be obtained as reported in the eCRF. The total EDs across all BAX 855 studies will be determined as the sum of EDs in current study and EDs in previous studies.
- The observation period for efficacy (OPE) in days in the study for subjects who never transferred to the surgery study is to be determined as:

$$OPE(Days) = (Stop\ Date - Start\ Date) + 1$$
 where "Start Date" refer to the first BAX 855 infusion in the current study and "Stop Date" to the last BAX 855 infusion in the current study. For subjects on the PK-guided regimen, first BAX 855 infusion will be the first prophylactic infusion.

• The OPE in days for subjects that did transfer to the surgery study is to be determined as:

$$OPE(Days)$$

$$= (Date\ of\ Transfer\ to\ Surgery\ Study - Start\ Date) + (Stop\ Date - Return\ Date\ to\ Current\ Study) + 1$$
where "Start\ Date" and "Stop\ Date" are\ defined\ as\ above.

• The OPE in weeks is to be determined from the OPE in days as:

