$$OPE(Weeks) = \frac{OPE(Days)}{365.2425} \times 52$$

• The OPE in months is to be determined from the OPE in days as:

$$OPE(Months) = \frac{OPE(Days)}{365.2425} \times 12$$

• The OPE in years is to be determined from the OPE in days as:

$$OPE(Years) = \frac{OPE(Days)}{365.2425}$$

- All OPE calculations to be performed overall and per treatment regimen.
- The average number of infusions per time period (weeks, months, years) is to be determined as the total number of infusions during the observation period divided by the duration for the particular time period (weeks, months, years).
- Total dose (IU/kg or IU as applicable) is to be determined as the sum of all doses, overall and by reasons for infusion, during the observation period in the current study.
- The average dose per time period (weeks, months, years) is to be determined as the total dose (IU/kg or IU as applicable) the subject received during the observation period in the current study, divided by the duration for the particular time period (weeks, months, years).
- Average dose per bleed is determined as the sum of all doses (IU/kg or IU as applicable) given to treat bleeding episodes divided by the number of bleeds observed for the particular subject in the current study.

Extent of exposure is to be summarized using descriptive statistics for the SAS, and PPAS and listed for the SAS. Summaries are to be presented by age category and treatment regimen at time of dose.

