- A bleed is considered to be a minor bleed if the severity is indicated as "Mild" or "Minor".
- A bleed is considered to be a weekday bleed if the bleed occurred on a Monday, Tuesday, Wednesday, Thursday or Friday.
- A bleed is considered to be a weekend bleed if the bleed occurred on a Saturday or Sunday.
- A bleed is considered to be a morning bleed if the bleed occurred between 04:00 and 11:59.
- A bleed is considered to be an afternoon bleed if the bleed occurred between 12:00 to 17:59.
- A bleed is considered to be a night bleed if the bleed occurred between 18:00 and 03:59.
- A bleed is considered to have occurred at an unknown time if the time of a bleed is not available.
- Time since last prophylactic infusion in hours is to be derived as:
  - $Time(h) = Date/Time\ of\ Bleed\ Start\ Date/Time\ of\ Infusion$  where the start date/time of infusion refers to the last prophylactic infusion received (other than to treat a bleed) prior to the start of the bleed. Time since last prophylactic dose is to be categorized as:
    - $\circ$  <24 hours.

```
24 - <48 hours.

48 - <72 hours.

72 - <96 hours.

>96 hours.
```

• Time since previous bleed are only to be determine if a subject had multiple bleeds and is to be derived as:

```
Time(months)
= (Date/Time \ of \ Current \ Bleed
- Date/Time \ of \ Previous \ Bleed)/365.2425 \times 12
```

- A bleed is considered to be treated with BAX 855 if at least one infusion linked to the particular bleed is present in the *Study Infusion* eCRF panels. Infusions to "Maintain Hemostasis" are not to be summarized as part of treatment for bleeding episodes.
- The number of bleeds per subject overall and by location (target joint, non-target joint, joint and non-joint), causality (spontaneous/unknown and injury), severity (mild, moderate and severe) and timing (weekends, weekdays, morning, evening and afternoon) are to be determined as the count of unique bleeds in each category a subject had during the observation period.
- Annualized bleeding rate (ABR) is to be derived for each treatment regimen the subject had during the study as:

$$ABR = \frac{Number\ of\ unique\ bleeds}{OPE\ (years)\ for\ treatment\ regimen}$$

The ABR is to be analyzed using a generalized linear model fitting a negative binomial distribution with logarithmic link function. Only subjects that have 100 or more EDs are to be included in the models, where total EDs are derived as in Section 6.7: Extent of Exposure.

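### Time when permitted ADVATE replaces BAX 855 prophylaxis stays in the BAX 855 observation period, with no on-product consumption denominator and no on-product ABR

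*Protocol*

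**What the plan says.** Protocol 10.4 withdraws a subject who takes any other FVIII concentrate after the first BAX 855 infusion, with one exception: "The use of (commercial) ADVATE may be permitted for a short period of time for administrative reasons". It gives no maximum duration and no rule for handling the data. SAP section 2 repeats the exception and continues: "It is also to be noted that ADVATE was allowed as rescue medication in" protocol versions before amendment four, under which some subjects enrolled.

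In SAP 6.7 the OPE start date is said to "refer to the first BAX 855 infusion in the current study", and the stop date is the last such infusion. On the PK-guided regimen the start is the first prophylactic infusion. The only deduction follows the sentence "The OPE in days for subjects that did transfer to the surgery study is to be determined as", and it drops the days between transfer to the surgery study and return. Consumption uses the same period: "The average dose per time period (weeks, months, years) is to be determined as the total dose" divided by its length.

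In SAP 7.1 the number of bleeds is "the count of unique bleeds in each category a subject had during the observation period", and ABR is that number over the OPE in years for the regimen. The models use the same count with log OPE as offset. The product in use at the time of a bleed is not a criterion.

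The possible major deviations for the per-protocol set (SAP 4.4) include "Use of any FVIII product other than ADVATE, as determined by the medical team", so ADVATE is carved out of that item.

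**The concern.** The co-primary efficacy objective and the secondary consumption objective are both about BAX 855. The plan acknowledges that some subjects may spend time on a different product, yet it has no rule for that time in either derivation.

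Consumption per month is the clearer problem. The denominator includes days on which ADVATE was given in place of BAX 855, while the numerator is meant to hold only BAX 855. For ABR, the bleeds and the time of such an interval both go to the subject's BAX 855 regimen, so the reported rate is a mixture. Nothing in the plan lets a reader see how much of a mixture: SAP 6.6 lists concomitant medications but does not summarise them, and no sensitivity analysis is planned.

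**Working it through.** The plan gives no figure to reproduce here, so the check applies the SAP formulas to assumed ADVATE intervals.

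**Inputs.** From the documents: planned participation of about 3 to 12 months (Protocol 8.3), taken as an OPE of T = 91, 182 or 365 days; 45 IU/kg twice weekly (Protocol 8.7.3.1), for illustration only; 365.2425 days per year (SAP 6.7); 5 days allowed between infusions on the twice-weekly regimen (SAP 6.8). Assumed, because the documents do not give them: t = 7, 14 or 28 days of substitution inside the OPE, and r, the bleed rate on ADVATE divided by the rate on BAX 855.

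**Consumption.** With f = t/T:

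- On-product: 45 × (2/7) × 365.2425/12 = 391.3 IU/kg per month.
- SAP formula: 45 × (2/7) × (T − t) ÷ (12T/365.2425) = 391.3 × (1 − f).

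| T (days) | t = 7 | t = 14 | t = 28 |
|---|---|---|---|
| 91 | 361.2 (−7.7%) | 331.1 (−15.4%) | 270.9 (−30.8%) |
| 182 | 376.3 (−3.8%) | 361.2 (−7.7%) | 331.1 (−15.4%) |
| 365 | 383.8 (−1.9%) | 376.3 (−3.8%) | 361.3 (−7.7%) |

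The shortfall is f whatever the dose. Two weeks in 52 gives 2/52 = 3.8%. Infusions per month fall by the same fraction.

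**ABR.** The subject's expected ABR is multiplied by 1 + f(r − 1).

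- f = 2/52, r from 0.7 to 2.0: 0.99 to 1.04.
- f = 14/182 = 0.077 and an assumed on-product rate of 2.00 per year: 1.92 (r = 0.5), 2.00 (r = 1), 2.15 (r = 2), 2.46 (r = 4).

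For a single subject with T = 182, t = 14 and one spontaneous bleed, the SAP gives 1 ÷ (182/365.2425) = 2.01. If the bleed began on ADVATE, the on-product ABR is 0. If it began on BAX 855, the on-product ABR is 1 ÷ (168/365.2425) = 2.17.

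**Does the under-75% exposure item catch it?** SAP 6.8 counts days since the last BAX 855 infusion beyond those allowed. Fourteen substituted days, starting 3.5 days after the last BAX 855 dose, make a gap of 17.5 days. That is 12.5 unexposed days, and exposure is (182 − 12.5)/182 = 93.1%. At T = 182, falling below 75% needs more than 0.25 × 182 = 45.5 unexposed days, or a single gap above 50.5 days.

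**Study level.** With equal subject weights, if 5% of subjects had f = 3.8%, mean consumption would shift by 0.05 × 3.8% = 0.2%. If 10% had f = 15.4%, the shift would be 1.5% and the mean ABR factor, with equal on-product rates, about 0.995 to 1.015 for r from 0.7 to 2.0. Both scenarios are assumptions.

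**The case against.** The strongest objection is about the estimand. In an open-label continuation study, counting every bleed over all follow-up in the full analysis set is a defensible treatment-policy choice. Missed doses stay in the OPE as well, and deleting bleeds from a co-primary count can look selective. This stands, and it is why the all-bleeds analysis should be kept.

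A reader might point to surgery-study time as a precedent for removal. The precedent is weak: Protocol 8.7.4 records data from those periods as part of the surgery study, whereas ADVATE days belong to this one.

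A reader might also infer that the per-protocol set gives no protection at all. That goes too far. SAP 4.4 separately lists exposure below 75% and compliance below 75%, and an ADVATE-only gap counts as unexposed time. These items only prompt a discussion, respond to large gaps, and leave the full analysis set unchanged.

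An isolated ADVATE rescue infusion before amendment four is a different case. BAX 855 prophylaxis may have continued throughout, and cutting the time up to the next BAX 855 dose would discard covered follow-up. Any rule has to separate rescue from substitution.

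Finally, the permission is narrow, and Protocol 9.3 allows discontinuation for repeated unjustified prophylaxis with another FVIII. A small overall effect is therefore plausible.

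**Conclusion.** The gap is real and modest. ADVATE-substitution time between the first and last BAX 855 infusion stays in the OPE, and bleeds in it count toward the BAX 855 regimen. For an affected subject, BAX 855 dose and infusions per month are understated by the ADVATE share of the OPE: 1.9% to 30.8% over the assumed grid, 3.8% for 2 weeks in 52. This assumes that ADVATE infusions are not entered in the Study Infusions panels. SAP 4.2 and the diary content in Protocol 10.5.1 make that likely, but the eCRF is not available. If they were entered there, consumption would mix two products instead.

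Two stronger readings are not supported. The shorter ADVATE half-life in Protocol 6.4.2 might suggest that ABR is biased upward. Those are single-dose data from 18 evaluable subjects, and Protocol 6.1 notes that conventional FVIII is infused more often, so r could lie on either side of 1. Nor can the co-primary result be called materially distorted: the number of subjects and days on ADVATE is not given, and the study-level effect may be small. ADVATE use before the first or after the last BAX 855 infusion is unaffected.

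**What to change.** In SAP 6.7, define an ADVATE-substitution interval as time when scheduled BAX 855 prophylaxis was replaced by ADVATE, running from the first substituted dose to the next BAX 855 infusion. Identify it from the concomitant-medication and infusion records. State that isolated ADVATE rescue infusions given while BAX 855 prophylaxis continued do not create an interval. Exclude these intervals from the denominator for BAX 855 dose and infusions per month, overall and by regimen.

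In SAP 7.1, keep the all-bleeds ABR on the full analysis set. Add a prespecified on-product ABR for spontaneous and for total bleeds, which removes the intervals from the OPE offset and removes bleeds with onset in them from the count. A bleed that began on BAX 855 stays in. Report the number of subjects, days and bleeds affected, so that a negligible effect can be seen to be negligible.

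The cost is some SAP wording, one small derivation from data already collected, and slightly less follow-up time for affected subjects in the on-product figures. Treatment and study conduct do not change.
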